4.8.1 Adverse Drug Reactions

Any adverse event (AE) which has a reasonable possibility of a causal relationship with the medicinal product will be considered as an Adverse Drug Reaction (ADR).

Adverse Drug Reactions (ADRs) will be coded by the Data Management of the CRO according to version stated in the DMP. Coding will be agreed upon with the Sponsor before database lock (cf. DMP).

All ADRs occurring after first VCP administration will be listed in appendix 16.2 of the report.

The analysis will include only treatment-emergent ADRs (TEADRs), i.e. all documented ADRs that started or worsened after the start of VCP infusion. It is assumed that for each increase in intensity of an ADR a new entry of the ADR will be done by the investigator; hence such cases will be analyzed like different phases of the same ADR.

A descriptive analysis will be performed. Incidences will be presented by primary system organ classes (SOC) and incidences of PT within primary SOC sorted according to the Internationally Agreed Order.

Multiple counts within a PT or SOC (repeated or different included terms or changes in descriptors) will be counted only once for the calculation of incidences.

Global incidences will be calculated for:

- All TEADRs irrespective of the causality assessment
- TEADRs by worst severity

A listing of "special cases" containing subject identification, age, sex, ADR descriptors, start and end of treatment will be prepared for the following types of TEADRs:

- Serious ADRs (SADRs)
- ADRs which led to death
- ADRs which led to discontinuation

Serious non-treatment emergent ADRs will be listed separately.

Statistical Analysis Plan	Version 3.0		Page 14 of 17
Sponsor	Octapharma	Protocol No	WIL-29

4.8.2 Other relevant Safety data

Other relevant safety information is any information relating to:

- Pregnancies
- Drug abuse
- Misuse
- Overdose
- Medication errors
- Interactions with other medicinal products or devices
- Occupational exposure associated with any VCP used during this study, even if no ADR occurred

Any data obtained on the mentioned other safety information will be listed in individual patient listings.

4.9 Other variables

Not applicable.

4.10 Interim analyses

Not applicable.

5 QUALITY CONTROL

The SAP was reviewed by the trial statistician (TS) before signature. Particularly, the TS has checked the consistency of the described methods and planned outputs with the actual version of the study protocol. In addition, a sponsor representative has reviewed the SAP before final approval.

Log files of all SAS® programs used in the analysis will be checked for errors, warnings and suspicious notes by the statistical programmer (SP). All findings will be either eliminated or commented upon. The final version of each program will be stored along with its log file in the electronic archive.

All programs will be validated by the program author or an independent statistical programmer depending on the requested validation level selected in the List of TLFs.

The agreement of the program outputs with the SAP, their consistency and plausibility will be checked by the TS. Moreover, the TS will review the outputs regarding completeness, readability and comprehensibility.

The described process is associated with the 'normal' level of program validation. Additional levels of quality control can be specified in the List of TLFs (see Appendix, 1) for individual outputs.

Statistical Analysis Plan	Version 3.0		Page 15 of 17
Sponsor	Octapharma	Protocol No	WIL-29

6 DERIVATIONS AND TRANSFORMATIONS

6.1 Formulas for derived variables

Variable	Description
Durations between two dates	Later date minus earlier date plus 1, expressed in days. (Remark: Duration will be 1, if both dates are the same.)
Surgery Period	(Date of surgery – date of last VCP treatment for surgery + 1)/365.25
Total Annualized Bleeding Rate (TABR)	Number of bleedings excluding menstrual bleedings / (date of study completion – date of screening + 1)/365.25 (Surgery periods, and BEs occurring within these surgery periods, will be excluded from the calculation of TABR. BEs occurring at day of surgery but prior to start of surgery/start of treatment for surgery will be included into calculation)
Spontaneous Annualized Bleeding Rate (SABR)	Number of spontaneous bleedings / (date of study completion – date of screening + 1)/365.25 (Surgery periods, and BEs occurring within these surgery periods, will be excluded from the calculation of SABR. BEs occurring at day of surgery but prior to start of surgery/start of treatment for surgery will be included into calculation)
Traumatic Annualized Bleeding Rate (TRABR)	Number of spontaneous bleedings / (date of study completion – date of screening + 1)/365.25 (Surgery periods, and BEs occurring within these surgery periods, will be excluded from the calculation of TRABR. BEs occurring at day of surgery but prior to start of surgery/start of treatment for surgery will be included into calculation)
Heavy Menstrual Bleeding Rate (HMBR)	Number of heavy menstrual bleedings* / (date of study completion – date of screening + 1)/365.25 (* for a definition refer to section 6.4)
ED	Exposure day = each calendar day the subject received VCP

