### **8.2 STUDY ENDPOINTS**

#### **8.2.1 Primary Endpoint**

The primary endpoint of this NIS is to characterise the total annualised bleeding rate (TABR) of patients with type 3, type 2 (except 2N), or severe type 1 VWD undergoing routine on-demand treatment with a VWF-containing product.

The TABR will be calculated as the total number of spontaneous, traumatic and other BEs in the time period between the start of data collection for each patient and the Study Completion Visit, divided by the duration (in years) between the start of data collection and the Study Completion Visit. Surgery periods, and BEs occurring within these surgery periods, as well as menstrual bleeds will be excluded from the calculation of TABR.

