2.2 Deviations from the trial protocol with regard to statistical analyses

For calculation of annualized bleeding rates (ABR) surgery periods will be subtracted from the time period under observation, and bleeding episodes occurred during surgery periods will not be counted as defined in protocol. However, the definition of surgery periods has been clarified. Protocol definition "3 hours before the start of surgery to the time the patient returns to

Statistical Analysis Plan	Version 3.0		Page 7 of 17
Sponsor	Octapharma	Protocol No	WIL-29

on-demand treatment" was updated to "day of surgery until last VCP treatment for surgery". Bleeding episodes that occurred on the day of surgery but before start of surgery will be counted towards the ABR.

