4.7.1 Primary Endpoint

Primary endpoint of this study is to estimate the total annualized bleeding rate (TABR) during on-demand treatment with any VCP.

TABR will be calculated as the total number of spontaneous bleeds, traumatic bleeds and other bleeds in the time period between screening visit and the study completion visit, divided by the duration (in years) between first dose of VCP and the study completion visit. Surgery periods, and BEs occurring within these surgery periods, will be excluded from the calculation of TABR. Menstrual bleeds will not be included in this calculation, but reported and analyzed separately.

Descriptive statistics for TABR along with exploratory 95% Confidence Intervals will be presented.

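### SAP 6.1 prints the Surgery Period with its two dates reversed, so a period of s days comes out as 2 − s days; the ABR formulas also need brackets and an explicit surgery term.

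*SAP*

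**What the plan says.** SAP 2.2 replaces the protocol's surgery period with "day of surgery until last VCP treatment for surgery" and states that "surgery periods will be subtracted from the time period under observation" when bleeding rates are annualised. The surgery date is therefore the start of the period and the last dose its end.

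The first row of the table in SAP 6.1 sets the rule for any duration between two dates: "Later date minus earlier date plus 1, expressed in days". The next row gives the Surgery Period, after an opening bracket, as "Date of surgery – date of last VCP treatment for surgery + 1)/365.25".

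TABR is printed in the same table as "Number of bleedings excluding menstrual bleedings / (date of study completion – date of screening + 1)/365.25". The SABR and TRABR rows have the same form. All three say in words that surgery periods are excluded, but none contains a surgery term. The heavy menstrual bleeding rate (HMBR) is "Number of heavy menstrual bleedings* / (date of study completion – date of screening + 1)/365.25", with no mention of surgery, although SAP 4.7.4 says it is calculated by analogy with TABR.

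In words, both documents divide by years. Protocol 8.2.1 has "divided by the duration (in years) between the start of data collection and the Study Completion Visit", and SAP 4.7.1 has "divided by the duration (in years) between first dose of VCP and the study completion visit".

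**The concern.** The Surgery Period row takes the earlier date minus the later one. That contradicts both the row above it and the definition in SAP 2.2. Because the result is then subtracted from observation time, the wrong sign lengthens exposure where it should shorten it.

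Section 6.1 is the derivation specification for the primary endpoint, and SAP 2.2 deliberately departs from the protocol's surgery period. The protocol therefore offers no formula to fall back on. The quality control in SAP 5 checks outputs for agreement with the SAP and for plausibility. Code that copies the printed row agrees with the SAP, and a patient's rate that is 5% to 10% low does not look odd. The rates are also meant as the on-demand side of a historical comparison with a prophylaxis study (Protocol 6.2), so they should be reproducible from the SAP.

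The brackets are a notation matter. Read from left to right, the ABR rows divide by days and then again by 365.25, where the text calls for division by years.

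**Working it through.** **The plan's own figure.** The only planning number is the 95% confidence half-width of ±0.8 for the mean ABR (Protocol 8.8, SAP 1.4). It reproduces: 1.96 × 3 / √55 = 0.793. The present point does not depend on it.

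**Inputs from the documents.** The Surgery Period formula and duration rule (SAP 6.1); the definition and the instruction to subtract (SAP 2.2); 55 patients (SAP 1.4); follow-up of around 6 months (Protocol 8.4.2).

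**Assumptions.** D = 183 days of follow-up, with 150 to 210 as a range. Lengths s and numbers of surgeries are illustrative because the documents give neither. Post-operative prophylaxis doses count as treatment for surgery. Each affected patient has one surgery period and at least one counted bleed.

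**Step 1: the day count.** For a period of s days the last dose falls s − 1 days after surgery.
- By the duration rule: (s − 1) + 1 = s.
- As printed: −(s − 1) + 1 = 2 − s, before division by 365.25.

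**Step 2: the denominator.** Correct: D − s. With the printed value subtracted: D − (2 − s) = D + s − 2. The excess is 2s − 2 days. The bleed count is the same in both, so the ratio of printed to correct TABR is (D − s) / (D + s − 2).

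| s (days) | Printed period (days) | Ratio at D = 183 | TABR too low by |
|---|---|---|---|
| 1 | 1 | 182/182 = 1.000 | 0% |
| 2 | 0 | 181/183 = 0.989 | 1.1% |
| 3 | −1 | 180/184 = 0.978 | 2.2% |
| 6 | −4 | 177/187 = 0.947 | 5.3% |
| 10 | −8 | 173/191 = 0.906 | 9.4% |
| 14 | −12 | 169/195 = 0.867 | 13.3% |

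Example: with 5 counted bleeds and s = 10, TABR should be 5 / (173/365.25) = 10.56. The printed period gives 5 / (191/365.25) = 9.56.

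**Step 3: other follow-up lengths.**
- s = 6: 144/154 = 0.935 at 150 days (6.5% low) and 204/214 = 0.953 at 210 days (4.7% low).
- s = 10: 140/158 = 0.886 at 150 days (11.4% low) and 200/218 = 0.917 at 210 days (8.3% low).

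**Step 4: the study mean.** With equal rates in all 55 patients and k of them having surgery, the shift is (k/55) × (1 − ratio), at D = 183:

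| | k = 1 | k = 5 | k = 10 |
|---|---|---|---|
| s = 6 | 0.10% | 0.49% | 0.97% |
| s = 10 | 0.17% | 0.86% | 1.71% |

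**Step 5: the brackets.** With 5 bleeds in 183 days and no surgery, the intended rate is 5 / (183/365.25) = 9.98. Read from left to right, 5 / 183 / 365.25 = 0.000075, smaller by a factor of 365.25² = 133,408. Nobody would miss that, which is why it is treated as notation only.

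**The case against.** The reversal is conceded on any reading; the case against concerns its weight.

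- **The meaning is already settled.** SAP 2.2 gives the order of the dates and the row above gives the rule. This stands: there is only one sensible reading, and a careful programmer may already have coded it correctly.
- **The route to harm is selective.** The printed ABR formulas contain no surgery term, so coding them literally never uses the Surgery Period. A programmer who subtracts it must be following the wording on exclusion, and SAP 2.2 has the dates in the right order. This is a fair point about likelihood. It does not make the printed row right, since a programmer can take the instruction to subtract from one place and the derived variable from the other.
- **A negative duration is easy to see.** True if the variable is inspected. The documents do not say that it is listed, and SAP 5 allows validation by the program's own author.
- **The effect is small and rests on assumptions.** This stands for the study mean. All inference is exploratory (SAP 4), and the top figure of 1.7% needs 10 of 55 patients with 10-day periods.
- **Long periods are not established.** Haemostatic therapy for 6 days or more is one of seven alternative criteria for major surgery (Protocol 8.5.6.1, SAP 4.7.3). It makes s of about 6 or more plausible, no more than that. If only doses coded 'Surgery' count, the last one normally falls on the day of surgery, s is 1, and the reversal has little effect.
- **Separate issues should not add weight.** Agreed. The TRABR numerator and the start date of the denominator are distinct contradictions. They appear under the fix only because they sit in, or bear on, the same formulas.

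**Conclusion.** The Surgery Period formula is wrong as printed and should be corrected. Coded literally and subtracted as SAP 2.2 directs, it makes TABR, SABR and TRABR too low for patients who have counted bleeds of the relevant type and a surgery period of 2 days or more. For TABR at 183 days of follow-up the error is about 5% at 6 days and 9% at 10 days. Everyone else is unaffected.

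The effect on the study mean is probably small, but it cannot be fixed from the documents because the number and length of surgeries are not given. All of these sizes assume that post-operative prophylaxis doses belong to the surgery period. The missing brackets and surgery term are gaps in notation whose intended content is clear from the text. The reason to act is that this table specifies how the primary endpoint is derived and the correction costs almost nothing.

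**What to change.** Rewrite the rows in SAP 6.1:

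- Surgery Period (days) = date of last VCP treatment for surgery − date of surgery + 1.
- TABR = N / {[(date of study completion − date of screening + 1) − sum of Surgery Period days] / 365.25}.
- SABR and TRABR in the same form. The TRABR numerator should be traumatic bleeds; the printed row says spontaneous.
- HMBR = N / [(date of study completion − date of screening + 1) / 365.25], with a statement of whether surgery periods are removed here too, given the analogy with TABR in SAP 4.7.4.

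Add two clarifications. First, state that the last VCP treatment for surgery includes doses recorded as 'Prophylaxis after surgery'. Second, reconcile the start of the denominator: SAP 4.7.1 uses the first VCP dose and SAP 6.1 uses screening. The formulas above keep screening, as SAP 6.1 prints it.

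The cost is a change of SAP wording and a check of the matching code lines. No new data are needed.

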### 8.5.3 Bleeding Episode (BE) Data

Study participants will be instructed by the investigator on recording BEs in their patient diaries. For any BE occurring during the study, whether treated or not, the following data will be recorded:

- BE type (spontaneous, traumatic, postoperative, menstrual, other)
- BE site
- BE severity (minor, major) (see **Table 4**)
- Date and time the BE first occurred or was first noticed
- Date and time the BE ended
- BE treated or not treated
- Data on the administration of the VWF-containing product (see **Section 8.5.4**)
- Assessment of the effectiveness of treatment at the end of the BE (see **Section 8.5.5**)

All of these parameters will be documented by the patient (together with the treating physician in case of on-site treatments) in the patient diary. Patients who experience a major BE should be treated at the treatment centre, if possible.

Based on these data, the frequency of BEs and the TABR and SABR under on-demand treatment will be calculated.

If the treatment of a BE in one bleeding site is interrupted for more than 48 hours, two separate BEs will have to be recorded; if, in addition to the original bleeding site, another bleeding site is affected, these events will be recorded as separate BEs at any time.

The severity of menstrual bleeding will be categorized as either 'minor' or 'major'. Thus menstrual bleeding of regular intensity classified as minor will be considered normal. Heavy menstrual bleeding will be regarded as a BE of 'major' severity (see **Table 4**).

BE severity will be assessed using the criteria given in **Table 4**.

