#### 8.5.6.2 Definitions of Surgery Periods and Time Points

- **Preoperative** is defined as the time period of up to 3 hours before the start of surgery.
- The **end of surgery** is defined as the time immediately after the last surgical suture.
- **Postoperative** is the period from the end of surgery to the time the patient returns to on-demand treatment.
- The **end of the postoperative period** is the time the patient returns to on-demand treatment.

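### SAP 6.1 lets postoperative-type bleeds outside the surgery period into the primary bleeding rate; SAP 4.7.1 and protocol 8.2.1 do not

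*SAP*

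**What the plan says.** Protocol 8.5.3 has each bleeding episode recorded under one of five types: "BE type (spontaneous, traumatic, postoperative, menstrual, other". Postoperative and other are separate entries.

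The TABR numerator is then stated three times:

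- Protocol 8.2.1: the "total number of spontaneous, traumatic and other BEs".
- SAP 4.7.1: the "total number of spontaneous bleeds, traumatic bleeds and other bleeds".
- SAP 6.1, the table of formulas for derived variables: "Number of bleedings excluding menstrual bleedings".

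All three places also apply a surgery exclusion. In SAP 6.1 it stands in the same cell as the formula: "Surgery periods, and BEs occurring within these surgery periods, will be excluded from the calculation of TABR". SAP 2.2 sets the surgery period as "day of surgery until last VCP treatment for surgery", in place of the protocol's end point, the return to on-demand treatment. Bleeds on the day of surgery but before its start are counted.

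SAP 2.2 is where statistical departures from the protocol are declared. It mentions the surgery period but not a change in the bleed types counted.

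**The concern.** Two texts that select by naming three types agree with a third that selects by removing one type only if there are four types in all. There are five. By type, SAP 6.1 keeps postoperative bleeds and SAP 4.7.1 does not.

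A programmer would naturally work from 6.1, because it is the table of formulas. The output check described in SAP 5 compares results with the SAP, and either numerator agrees with some part of the SAP. The discrepancy could therefore pass unnoticed.

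The 6.1 count can only equal or exceed the 4.7.1 count. The study's stated purpose (protocol 6.2) is to provide an on-demand bleeding pattern for historical comparison with a prophylaxis study. Any difference would thus raise the on-demand comparator rate, and it would do so through bleeds that follow surgery.

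**Working it through.** **The plan's own figure.** SAP 1.4 and protocol 8.8 give a half-width of ±0.8 for the mean ABR, with n = 55, SD = 3 and a 95% z interval. Check: 1.96 × 3 / √55 = 5.88 / 7.416 = 0.793, which rounds to 0.8. The figure is reproduced. It does not depend on the numerator wording and serves here only as a yardstick.

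**Which bleeds differ.**

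| Type (protocol 8.5.3) | Protocol 8.2.1 and SAP 4.7.1 | SAP 6.1, by type |
|---|---|---|
| Spontaneous | counted | counted |
| Traumatic | counted | counted |
| Other | counted | counted |
| Postoperative | not counted | counted |
| Menstrual | not counted | not counted |

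The difference is the postoperative type alone. The surgery exclusion common to both SAP sections then removes every bleed inside a surgery period, whatever its type. What remains is a bleed that is typed postoperative and lies outside the SAP surgery period. The text leaves two routes to that:

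1. The bleed starts after the last product dose given for surgery, which is where SAP 2.2 ends the period.
2. No product was given for the surgery, so the period has no end date under SAP 6.1. SAP 3.3 limits the surgery set to procedures treated with product before surgery, so the SAP does not assume that every surgery is treated.

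**Size per bleed.** Follow-up is about 6 months (protocol 8.4.2), so T = 0.5 year.

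- Effect on that patient's TABR: 1 / T = 1 / 0.5 = 2.0 per year.
- If 7 or 14 surgery days are subtracted (assumed values): 365.25 / (182.625 − 7) = 2.08 and 365.25 / (182.625 − 14) = 2.17 per year.
- Effect on the mean of 55: 2.0 / 55 = 0.036 per year (0.038 to 0.039 with the surgery days subtracted).
- Share of the half-width: 0.036 / 0.793 = about 5%.
- Number of such bleeds that would move the mean by one full half-width: 0.793 × 55 × 0.5 = 21.8, so about 22.

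**Size in total.** For k such bleeds the shift in the mean is k × 0.0364. The documents give no value for k, so the following is an assumed range: k = 0 gives 0, k = 1 gives 0.04, and k = 3 gives 0.11 per year.

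SAP 4.7.1 and 6.1 also state the start of the denominator differently. That is a separate matter. The same T is used for both here so that only the numerator differs.

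**The case against.** **Reach.** A reader might infer from the 6.1 formula that every non-menstrual bleed, and so every postoperative one, enters TABR. The documents do not support that. The same table cell excludes bleeds within surgery periods, and most postoperative bleeds would probably drop out under either definition.

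**Whether the remainder exists.** Protocol 8.5.6.2 says that postoperative "is the period from the end of surgery to the time the patient returns to on-demand treatment". If the diary label followed that definition, a bleed after the return to on-demand treatment would be typed spontaneous, traumatic or other and counted under both texts. This narrows the gap but does not close it. Protocol 8.5.3 does not tie the bleed type to that definition, SAP 2.2 has moved the end point, and surgery without product is not covered.

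**Whether 'other' is a catch-all.** If the endpoint's third term were meant to include postoperative bleeds, the two numerators would agree. But the endpoint uses the terms of the type list, where the two are separate. If a catch-all was intended, the SAP has to say so.

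**Coherence.** The time after the last surgical dose is not subtracted, so it counts as on-demand observation. Counting the bleeds in that time is a defensible convention. This objection stands in part: it shows that aligning 6.1 with 4.7.1 has a small cost. It does not make the two texts agree.

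**Materiality.** The analysis is descriptive, and no test or threshold in this study depends on the difference. SAP 4.7 already describes bleeds by type, and SAP 4 lists all subject data. This stands, and it limits the weight of the point.

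**Conclusion.** The SAP gives the primary endpoint two numerators. The 6.1 version can depart from protocol 8.2.1 without a declared deviation. The departure is confined to bleeds typed postoperative that fall outside the SAP surgery period.

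Each such bleed is worth about 2.0 per year for the patient concerned and about 0.036 per year on the mean of 55, assuming six months of follow-up. The number of such bleeds is not given and may be zero, so the effect on the mean is probably small. A reader might apply the per-bleed figure to five or ten such bleeds and conclude that a large part of the ±0.8 is at risk. Nothing in the documents supports counts of that order. Nor do the documents show which numerator was programmed.

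Confidence is high that the wording conflicts. There is no basis for claiming a material effect on the mean TABR. The point should still be corrected, because a primary endpoint needs one numerator.

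**What to change.** In the TABR row of SAP 6.1, replace the numerator with a count of bleeding episodes typed spontaneous, traumatic or other, so that it matches SAP 4.7.1 and protocol 8.2.1. Keep the surgery exclusion as it stands. Report postoperative-type bleeds outside surgery periods separately, as a count with the patients concerned.

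Add one sentence that acknowledges the consequence: observation time after the last surgical product dose stays in the denominator, while postoperative-type bleeds in that time are not counted. The same sentence can say how a surgery with no product given is handled.

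The cost is a line or two of SAP wording and one short output. No new data are needed, because bleed type is already recorded under protocol 8.5.3.

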### 8.5.2 Medical History and Prior Medications

The medical history as well as prior and concomitant medications will be obtained by patient interview. Records of past diseases and treatments (e.g., hospital discharge letters) will be obtained for the study files, if available.

VWF activity using VWF:RCO, VWF:Gp1bM, VWF:Gp1bR, or any other pertinent method will be recorded, as will VWF:Ag, the VWF multimer pattern for VWD type 2A, and the genotype for VWD type 2B, if available.

In addition, the age at first treatment for VWD and information on on-demand treatment with VWF-containing product in the previous 6 months before enrolment will be collected. Patients should preferably have a record of at least 5 spontaneous BEs requiring treatment in the past 3 months before screening. If this is not the case, the investigator should assess whether the patient experiences frequent enough bleedings to be included in the study.

For female patients of child-bearing potential, the birth control measures used within 6 months before enrolment will be documented. For all female patients, any history of heavy menstrual bleeding will be recorded.

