4.7 Efficacy

The analysis of the efficacy of on-demand treatment with VCP will be based on the FAS and additionally on the PP set if these populations differ by >5%.

Primarily, all obtained data on treatment characteristics (VCP dosages, frequencies, total consumption) and BEs (site, type, duration, frequency, efficacy assessment) will be described by providing summary statistics.

For the efficacy analysis on bleeding episodes by site of bleeding a separate site category for 'Nose' will be generated. Assignment to this category will be based on the collected verbatim for 'Other site, specify' (e.g. Nose bleed, Epistaxis or similar meaning).

Bleeding episodes that are ongoing at screening visit but started prior to screening will be captured in study database and will be listed, but will be excluded from efficacy analysis.

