4.7.2 Secondary Endpoints

Secondary endpoints are:

- Spontaneous annualized bleeding rate (SABR), calculated in analogy with TABR
- Data on the consumption of VCP product (VWF/FVIII IU/kg per month per patient) used for routine on-demand treatment

The following secondary efficacy endpoints will be studied except in Croatian centers:

- Effectiveness of VCP in the treatment of BEs based on the proportion of successfully treated BEs (definition see section 6.2)
- Effectiveness of surgical prophylaxis with VCP based on the proportion of successfully treated surgeries (definition see section 6.3)
- Pictorial Blood Loss Assessment Chart (PBAC) score

Regarding the VCP administration data, the following parameters will be documented:

- Dates and times of VCP injections
- Doses of VCP in IU and IU/kg and VCP batch numbers
- Reason for VCP injection (prophylaxis, treatment of BE, surgery)

Statistical Analysis Plan	Version 3.0		Page 12 of 17
Sponsor	Octapharma	Protocol No	WIL-29

Descriptive statistics will also be presented for the SABR and for time in study, exposure days, number of infusions and dosages of VCP overall and by reason for VCP injection.

Additionally, descriptive statistics will be presented for the traumatic annualized bleeding rate (TRABR), calculated in analogy with TABR.

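### SAP 6.1 defines the traumatic annualised bleeding rate (TRABR) with a count of spontaneous bleeds, so as written it equals the spontaneous rate (SABR) for every patient

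*SAP*

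**What the plan says.** SAP 6.1 lists the formulas for the derived bleeding rates. The formula "Number of spontaneous bleedings / (date of study completion – date of screening + 1)/365.25" appears there twice, first in the SABR row and then in the TRABR row. The second occurrence does belong to TRABR: the row is labelled as the traumatic rate, and its note says that surgery periods and the bleeds within them "will be excluded from the calculation of TRABR".

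SAP 4.7.2, after its list of secondary endpoints, adds that "descriptive statistics will be presented for the traumatic annualized bleeding rate (TRABR), calculated in analogy with TABR". SAP 4.7.1 defines the numerator of TABR as the "total number of spontaneous bleeds, traumatic bleeds and other bleeds", so spontaneous and traumatic bleeds are separate components of the total. Protocol 8.5.3 likewise records spontaneous and traumatic as distinct types for each bleeding episode.

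**The concern.** A rate labelled traumatic has a numerator that counts only spontaneous bleeds. The pattern suggests that the SABR row was copied and the acronym in the note updated, but one word in the numerator was not.

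SAP 4.7.2 describes TRABR by analogy only, so SAP 6.1 holds its only explicit formula. The paragraph on listings in SAP section 4 says that listed derived data will be stored permanently and calculated as the SAP sets out. A programmer working from the table would therefore store and report the spontaneous rate under a traumatic label.

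The primary objective is to characterise the bleeding pattern, and protocol 6.2 says that the data will serve historical comparisons with a prophylaxis study. A mislabelled rate could be carried into that use.

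**Working it through.** **Comparison of the two rows in SAP 6.1**

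| Element | SABR row | TRABR row |
|---|---|---|
| Label | Spontaneous | Traumatic |
| Numerator | Spontaneous bleedings | Spontaneous bleedings |
| Denominator | Screening to study completion, plus 1 day, with 365.25 | Same |
| Surgery periods and bleeds within them | Excluded | Same |
| Bleeds on the day of surgery, before it starts | Included | Same |

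Numerator, denominator and exclusions are identical, so literal TRABR = SABR for every patient. This needs no assumption about the data. It also holds however the denominator is read, because both rows share it.

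**Size of the error**

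The documents state no TRABR value and no traumatic bleed rate, so there is no figure to reproduce and the counts below are assumed. The inputs are:

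- Follow-up of 183 days, an assumption based on the roughly 6 months in protocol 8.4.2.
- No surgery period, and a denominator read as days/365.25.

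Years of observation = 183/365.25 = 0.501, so one bleed = 1/0.501 = 2.00 per year.

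Error in TRABR = (spontaneous count − traumatic count)/(183/365.25), or about 2.00 × (spontaneous − traumatic).

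| Spontaneous | Traumatic | TRABR as written | TRABR as intended | Error |
|---|---|---|---|---|
| 4 | 1 | 7.98 | 2.00 | +5.99 |
| 0 | 2 | 0 | 3.99 | −3.99 |
| 2 | 2 | 3.99 | 3.99 | 0 |
| 10 | 1 | 19.96 | 2.00 | +17.96 |

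Errors are calculated before rounding. The last row is an upper illustration. Protocol 8.5.2 prefers patients with a record of "at least 5 spontaneous BEs requiring treatment in the past 3 months before screening"; keeping that rate for 6 months gives about 10 spontaneous bleeds. It is a preference only, and the investigator may enrol patients who do not meet it.

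**Coherence with TABR**

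With 4 spontaneous bleeds, 1 traumatic bleed and no others, TABR = 5/0.501 = 9.98. SABR plus TRABR as written is 7.98 + 7.98 = 15.97 (before rounding), so two components would exceed their total. With the traumatic count, 7.98 + 2.00 = 9.98, as it should be.

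**The case against.** The strongest reply is that this is an evident slip with little reach. The row label and SAP 4.7.2 show what is meant, and SAP 4.7.2 read with SAP 4.7.1 does supply a rule of its own, so a programmer reading the whole SAP would probably count traumatic bleeds. TRABR is not a protocol endpoint, stands outside the SAP's endpoint list, and is not among the subgroup analyses in SAP 3.4. The analysis is descriptive. SAP 4.7 also states that "BEs (site, type, duration, frequency, efficacy assessment) will be described by providing summary statistics", so the distribution of bleed types would be reported in any case. Finally, SAP 5 provides that "The agreement of the program outputs with the SAP, their consistency and plausibility will be checked by the TS", and a TRABR table identical to the SABR table ought to be noticed.

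Most of this stands, and it limits the importance of the point. It does not remove the error. SAP 4.7.2 offers an analogy while SAP 6.1 offers a formula, and the two conflict. The output check is partial protection: consistency and plausibility might expose the duplicate, but a program that follows SAP 6.1 literally would agree with that section. The trial statistician and a sponsor representative were also to review the SAP before signature and approval, yet the wrong word is in version 3.0.

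It is also fair to say that the numerical examples rest on assumed counts. They show the direction and possible range of the error, not its expected size.

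**Conclusion.** The concern holds. The TRABR formula in SAP 6.1 is wrong as written and returns SABR for every patient; that follows from the text alone. Under the stated assumptions (183 days, no surgery, days/365.25), the error is 2.00 per year for each bleed by which the spontaneous and traumatic counts differ, and it is zero only when they are equal. It runs upward where spontaneous bleeds predominate and downward where traumatic bleeds do.

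The damage is confined to one additional descriptive output and its stored variable. TABR and SABR are unchanged. The point should be fixed before programming, but it does not threaten the primary analysis.

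**What to change.** In the TRABR row of SAP 6.1, change the numerator to the number of traumatic bleedings. Keep the observation-time denominator and surgery rules the same as for TABR and SABR. SAP 4.7.1 and SAP 6.1 start the denominator at different points (first dose of product and screening, respectively); that is a separate matter which affects the rates alike, and however it is settled TRABR should follow.

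A per-patient check that the component rates sum to TABR would catch this kind of slip. If one is added, it should use the SAP 4.7.1 numerator (spontaneous, traumatic and other). The SAP 6.1 numerator for TABR counts all non-menstrual bleeds and may include postoperative ones, so it would have to be reconciled first.

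The cost is a one-word SAP correction. Protocol 8.5.3 already collects the type of each bleed, so no new data are needed.
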